- Comparison of the following variables between the groups: granulation tissue integrity including hypergranulation state, time to close, flap/graft take, dehiscence, and reoccurrence.

Objective 2

To compare bacterial load, quantitative cultures, and clinical infections in wounds treated with NPWT PRO compared to wounds treated with NPWT PRO with simultaneous irrigation.

H1: Bacterial load measured with quantitative polymerase chain reaction (qPCR) will be progressively lower with continuous irrigation.

H2: Patients treated with simultaneous irrigation and NPWT PRO will have fewer infections defined by qPCR and clinical criteria.

Primary Endpoint:

- Comparison of reduction in bacterial load in wounds treated with NPWT and NPWT with simultaneous irrigation.

Secondary Endpoints:

- Comparison of incidence of infection in wounds treated with NPWT and NPWT with simultaneous irrigation.
- Infection-induced necrosis
- Infection reoccurrence post-closure

Objective 3

Assess changes in molecular markers associated with wound healing and regeneration of healthy tissue.

H1: NPWT PRO with simultaneous Irrigation will improve the levels of growth factors, cytokines, and other molecular markers over NPWT PRO alone.

H2: Negative pressure wound therapy will drive molecular changes in growth factors and other cytokines associated with regeneration of healthy tissue.

Primary Endpoint:

- To compare changes in genes and other molecular markers associated with wound healing between wounds treated with NPWT and NPWT with simultaneous irrigation.

Secondary Endpoint:

- To compare the addition of simultaneous irrigation on gene expression and expression of molecular markers from baseline.

Objective 4

Quality of Life and Patient Satisfaction Analyses

H1: Patients treated with the NPWT PRO device will show greater patient satisfaction with treatment than those treated with KCI Ultra NPWT therapy.

Primary Endpoints:

- To compare Quality of Life and Patient Satisfaction between patients treated with NPWT PRO versus patients treated with KCI Ultra NPWT therapy.
- To compare Quality of Life and Patient Satisfaction between patients with wounds treated with NPWT PRO versus NPWT PRO + SI.
- Evaluate functional status, using the Short Form 36 (SF36). These will be administered at baseline and at the last study visit.

Subjects and Recruitment

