If evaluation of the clinical indicators suggest the presence of significant bacterial infection of the wound, swab culture, utilizing swab technique [126] will be performed to confirm or reject the presence of significant bacterial infection severe enough to warrant the subject terminated from the study. The swab culture will be performed using a laboratory-provided swab that is pressed down over a 1 cm² area of the wound that is then delivered to the lab for analysis to determine Colony-Forming Units (CFUs) per gram of viable wound tissue and beta-hemolytic Streptococcus per gram of tissue. The findings of a positive or negative swab culture utilizing Levine's technique will be interpreted according to the following criteria:

- Positive culture indicating presence of bacterial infection: $\geq 1,000,000$ Colony-Forming Units (CFUs) per gram of viable wound tissue OR containing beta-hemolytic Streptococcus per gram of tissue at any level.
- Negative culture indicating absence of bacterial infection: $< 1,000,000$ Colony-Forming Units (CFUs) per gram of viable wound tissue OR no beta-hemolytic Streptococcus per gram of tissue at any level.

Tissue specimens will be obtained from the chronic wounds using 1) wound exudate, 2) broad Z-technique, and 3) Levine technique [126]. Acquisition of swab specimens was followed with a wound tissue biopsy. The diagnostic validity of each technique was determined by associating the quantitative culture findings of each swab specimen with the culture findings of concurrent tissue specimen (gold standard). Levine's technique performed best of the three swab techniques in terms of all four validity parameters: sensitivity was, specificity, positive predictive value, and accuracy.

Bio-burden

Bio-burden will be assessed using qPCR to quantify bacterial load from serial tissue specimens. Specific organisms that will be quantified using qPCR are listed in the table below. Bone, soft tissue will be sent to Research and Testing Laboratory (Lubbock, TX) for analysis.

Specific organisms (and two resistance factors) to be quantified using qPCR.			
E. faecalis	E. faecium	S. epidermidis	M. morgani
K. pneumonia	S. aureus	C. striatum	S. haemolyticus
S. agalactiae	S. marcescens	F. magna	S. mutans
S. pyogenes	H. influenzae	P. mirabilis	Vancomycin res.
C. albicans	M. catarrhalis	C. parapsilosis	Methicillin res.
P. aeruginosa	S. pneumoniae	A. baumannii	Total Bioburden

Osteomyelitis

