 - The subject will re-enter the therapy administration phase including the weekly or standard of care efficacy and safety evaluation test site visits and procedures.

Home Health Visits

The study therapy will only be given while the subject is in the hospital. If the subject's wound is not ready for closure during the hospital stay, the subject will continue NPWT at home. NPWT at home will be without irrigation. If the subject continues to receive NPWT after hospital discharge, the subject will be seen twice weekly by a home health nurse for dressing changes. The home health nurse will collect sitting blood pressure and pulse rate. Amount, type and character of wound drainage will be documented, as well as any adverse events and changes to concomitant medications. Offloading will be reapplied after dressing changes. At the same time, subject will continue to be followed by the study doctor during regular post-operative visits at outpatient clinic. If the wound closes, End of study visit will be performed and she/he will see the study doctor at outpatient clinic to have the closed wound checked.

Safety and Efficacy Evaluation

During the study therapy administration and evaluation phase, the subject will attend once weekly or standard of care test site visits, commencing at the end of Week 1 of therapy administration and ending at the weekly or standard of care visit where the wound is determined ready for surgical closure and the therapy administration process is complete.

- Weekly or standard of care Efficacy Evaluations
 - Digital Photography of the Study Wound
 - Wound Measurement (using a ruler and the eKare Insight System)
 - Granulation Tissue Estimation
 - Additionally, at the final week of efficacy evaluation test site evaluation, Subject Satisfaction with Study Procedure Outcome Evaluation will be performed.
- Weekly or standard of care Safety Evaluations
 - Safety Measures
 - Debridement Indication
 - Degree of Pain Rating
 - Infection Evaluation: encompassing swab culture and osteomyelitis assessment, if indicated.
- Inpatient Tissue Samples
 - Tissue samples will be taken and kept, for research, at inpatient study visits prior to wound closure for the following analyses.
 - For bacterial analyses
 - For gene expression analyses
 - After wound closure, no samples will be taken unless wound reoccurrence occurs.
 - Samples will be approximately 0.25-0.5 cm³ in size

- Bio-burden: qPCR evaluation
- Other Activities

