Wound Assessment/ Debridement	X	X	X		X		
Tissue /bone ¹ / wound culture samples for qPCR cultures & bioburden analysis		X	X (Subsequent surgery)				

			while Inpatient)				
NPWT/NWPT (i) randomization/dressing application/changes		X	X	X (Weeks 2-4)	X (Weeks 2-4)		NWPT for maximum 4 weeks after baseline(Day0 surgery) if wound is not closed in the hospital
SF-36 Questionnaire	X					X	
Hyperspectral Imaging Analysis	X						To occur prior to surgery
Discharge Instructions			X		X		
Offloading			X	X	X		At hospital discharge & continuing to Week 12
Adverse Events		X	X	X	X	X	
Current/concomitant antibiotics	X	X	X	X	X	X	
Wound imaging/measurement		X	X		X	X	While active study wound is present
Neuropathy Disability Score in Patients with Diabetes	X						

¹ Only if performed as a necessary part of standard of care.

² Subjects who heal before week 12 will exit the study and complete EOS visit.

Biostatistics

Sample Size Justification:

There are no published data with the Cardinal PRO negative pressure wound therapy (NPWT) device with or without irrigation in order to determine an estimate of the sample size for this study. One of the purposes of this project is to obtain data, so we can power a larger multicenter study. Even though the KCI NPWT device with irrigation has been commercially available, there is little data about volume change or wound healing in the population we are studying.

The previous sample size justification was based on a comparison of the proportion of wounds expected to achieve surgical closure. The proportion of subjects with closed wound was 62% using traditional KCI NPWT and 94% using NPWT with periodic irrigations with Prontosan. For the sample size, we estimated 85-90% wound closure with NPWT with irrigation and 60% wound closure with NPWT without irrigation. We assume the NPWT devices (KCI and Cardinal) without irrigation would have similar results.

Equations

The following formula was used to estimate the required sample size, n , for the relative difference in proportions P_1 and P_2 .

$$n = \frac{\left(Z_{\alpha/2} \sqrt{2P(1-P)} + Z_{\beta} \sqrt{P_1(1-P_1) + P_2(1-P_2)} \right)^2}{(P_1 - P_2)^2}$$

where

$$P = \frac{P_1 + P_2}{2}$$

Using the formula above and assuming 90% wound closure with NPWT with irrigation and 60% wound closure with NPWT without irrigation and a type I error of 0.1, the required sample size is about 25. If a Type I error of 0.05 is assumed, then the required sample size is about 31.

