As the relative difference gets smaller, the required sample size increases. The two tables below show estimates for sample size for values of alpha of 5% and 10% for five values of P_2 .

P_1	P_2	rel. difference	$\alpha/2$	β	power	n
0.6	0.9	-0.75	.05	0.200	0.800	25
0.6	0.89	-0.73	.05	0.200	0.800	27
0.6	0.88	-0.70	.05	0.200	0.800	29
0.6	0.86	-0.65	.05	0.200	0.800	35
0.6	0.85	-0.63	.05	0.200	0.800	41

P_1	P_2	rel. difference	$\alpha/2$	β	power	n
0.6	0.9	-0.75	.025	0.200	0.800	31
0.6	0.89	-0.73	.025	0.200	0.800	34
0.6	0.88	-0.70	.025	0.200	0.800	37
0.6	0.86	-0.65	.025	0.200	0.800	45
0.6	0.85	-0.63	.025	0.200	0.800	51

PRELIMINARY DATA: Kim PJ, Attinger CE, Steinberg JS, Evans KK, Powers KA, Hung RW, Smith JR, Rocha ZM, Lavery L. The impact of negative-pressure wound therapy with instillation compared with standard negative-pressure wound therapy: a retrospective, historical, cohort, controlled study. *Plast Reconstr Surg.* 2014 Mar;133(3):709-16.

This study shows that NPWT with two different doses of Prontosan irrigation solution decreases the number of surgeries, length of hospitalization, and increases the proportion of wounds that are closed compared to “traditional NPWT”. We conducted a retrospective study of hospitalized patients with infected lower extremity wounds that received NPWT without irrigation (n=74), NPWT with irrigation with polyhexanide biguanide (PHMB) with a 6 minutes dwell time (n=34), and NPWT with irrigation with polyhexanide biguanide (PHMB) with a 20 minute dwell time (n=34). The proportion of wounds that were surgically closed was significantly higher, and the number of surgeries was significantly less in patients that received NPWT with 6 minutes of irrigation compared to standard NPWT without irrigation. Similar trends were seen with NPWT with 20 minutes of irrigation.

Table 1	NPWT n=74	NPWT 6 minute irrigation n=34	NPWT 20 minute irrigation n=34
Number of Surgeries	3.0 ± 0.9	2.4 ± 0.9 p=0.04	2.6 ± 0.9 p=0.003
Length of Stay (days)	14.9 ± 9.2	11.9 ± 7.8 p=0.10	11.4 ± 5.1 p=0.03
Time to Final Surgical Procedure	9.23 ± 5.2	7.8 ± 5.2 p=0.04	7.5 ± 3.1 p=0.002
Percent Closed	62%	94% p<0.001	80% p=0.08

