The inpatient stay and post-operative visits are covered under a 90-day global payment which is inclusive of all procedures, devices, testing and ancillaries associated with the surgical procedure, including NPWT. Subjects’ insurance will not be charged any additional amount for the NPWT devices used in the study. The KCI devices are standard at Parkland; Cardinal is providing their devices. But again, in neither situation would a subject or their third party pay or be charged anything additional.

Survival Analyses Models

The primary analytical method presented in this report is based on a time-to-event strategy using Kaplan-Meier estimates, followed by a log-rank test. This statistical procedure provides a comparison of the distribution of events between the 2 treatment groups. In addition to the event rates calculated for the post-baseline time points, the median time to 100% closure, 75% closure, and 76-100% wound bed granulation will also be calculated. This same methodology will also be used to compare the overall duration of treatment, and within the individual patient subsets defined by their outcome status.

A Cox proportional hazard model will be used to relate time to specific events to various risk factors. The main modeling strategies will look at the time to adverse events with time being measured from the time of surgery or the time of NPWT application until either an adverse event occurs, the patient is considered healed, or the end of the study. Cox proportional hazard model allows the independent variables to be continuous covariates or categorical or binary factors. The type of NPWT treatment will be the main independent variable. We will use multivariate proportional hazard regression analysis methods to investigate what factors are significant for non-healing patients or patients that have complications. Similar to the logistic regression, maximum likelihood estimates of model parameters along with tail probabilities (p-values) and confidence intervals for parameters

will be derived based on asymptotic inferences. For the proportional hazard model the ratio of the hazards for two subjects one with and one without diabetes, given that the subjects have the same values for other parameters can be estimated from the model coefficients. Repeated measures ANOVA and ANOVA will be used to evaluate changes in quantitative cultures and laser Doppler measurements over time and between treatment groups.

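### The Objective 2 primary endpoint, reduction in bacterial load, has no fixed time point, and its follow-up specimens fall on days set by wound course and hospital stay, which the stated ANOVA does not accommodate

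*Combined protocol and SAP*

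**What the plan says.** **Endpoint.** Under Objective 2 the primary endpoint is "Comparison of reduction in bacterial load in wounds treated with NPWT and NPWT with simultaneous irrigation". No time point follows. The first hypothesis is that load by qPCR "will be progressively lower with continuous irrigation", so a time course is intended.

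**Specimens.** The Bio-burden section says "Bio-burden will be assessed using qPCR to quantify bacterial load from serial tissue specimens", without number or days. Under Safety and Efficacy Evaluation: "Tissue samples will be taken and kept, for research, at inpatient study visits prior to wound closure for the following analyses". It adds: "After wound closure, no samples will be taken unless wound reoccurrence occurs". The Schedule of Events marks the qPCR row at Day 0 and in the Week 1 inpatient column (which may run into Week 2), there qualified as "Subsequent surgery" while inpatient. No later column is marked.

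**What triggers repeat surgery.** The Standard of Care Regimen allows debridement only when indicated; the indications include necrotic tissue and infection. Surgical closure is a separate operating-room procedure, done once the wound is judged ready (Therapy Administration).

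**Analysis.** Survival Analyses Models says: "Repeated measures ANOVA and ANOVA will be used to evaluate changes in quantitative cultures and laser Doppler measurements over time and between treatment groups". It lists no occasions, no rule for choosing the follow-up specimen and no handling of subjects with Day 0 only. The Microbial Diversity section separately assigns the qPCR bio-burden results to multivariate methods based on distances between samples.

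**The concern.** A reduction needs two measurements a defined interval apart. Here the interval is whatever the clinical course makes it. On the Schedule's reading, load is measured again when the wound needs further debridement or is ready to be closed, and a subject discharged without another operation is not measured again. On the broader reading of the sampling text, the last possible day is still the day of discharge or closure, which varies by subject.

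If the arms differ in surgical course or length of stay, they will differ in specimen timing and availability even when bacterial decline is identical. At stake are the primary result of Objective 2 and the stated aim (Innovation) of learning how long eradication takes. Because no rule selects the follow-up specimen, it could also be chosen after the data are seen.

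**Working it through.** **1. Plan's own figure.** None belongs to this endpoint. The only sample size is for surgical closure, 60% against 90%. The printed formula gives 31.5 (stated 31) at two-sided 5% and 24.7 (stated 25) at 10%, so it reproduces, but it says nothing about bacterial load.

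**2. The plan applied literally.** Assume the same decline, 0.2 log10 per day, in three subjects.
- A: further surgeries on Days 5 and 11. Last-specimen reduction = 11 × 0.2 = 2.2 log10.
- B: closed in hospital on Day 6. Reduction = 6 × 0.2 = 1.2 log10.
- C: discharged on home NPWT without another operation. No reduction can be calculated.

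Identical biology gives 2.2, 1.2 and missing. Classical repeated measures ANOVA has no common occasions on which to align A and B, and cannot use C.

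**3. Could timing and availability differ by arm?** The inputs are from Table 1 of the Sample Size Justification (retrospective data).
- Number of surgeries: 3.0 (NPWT), 2.4 (6-minute irrigation), 2.6 (20-minute); SD 0.9 in each.
- "Time to Final Surgical Procedure": 9.23 ± 5.2, 7.8 ± 5.2 and 7.5 ± 3.1. No unit is printed; read here as days.

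Assume counts are roughly normal and include the first debridement. The share with no second surgery is Φ((1.5 − mean)/0.9):
- NPWT: Φ(−1.67) = 5%
- 6-minute: Φ(−1.00) = 16%
- 20-minute: Φ(−1.22) = 11%

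The same table points the other way on closure: 62% closed with NPWT against 94% (6-minute) and 80% (20-minute). Closure in hospital is itself a subsequent surgery, so irrigation could yield more follow-up specimens. Availability may differ by arm, but the sign is open.

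**4. Effect of timing alone.** The gap in time to final procedure is 9.23 − 7.8 = 1.43 days (6-minute) and 9.23 − 7.5 = 1.73 days (20-minute). With an equal decline r in both arms and last-specimen change, the expected false difference is r × gap. For the 6-minute gap, r = 0.1 to 0.3 log10 per day gives 0.14 to 0.43.

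An unlimited normal with SD 5.2 puts some procedures before Day 0 and some after Day 14, outside the inpatient window. Truncating to Days 1-14, the mean is μ + σ[φ(a) − φ(b)]/[Φ(b) − Φ(a)], with a = (1 − μ)/σ and b = (14 − μ)/σ:
- NPWT: 9.23 + 5.2 × (0.114 − 0.262)/0.764 = 8.22
- 6-minute: 7.8 + 5.2 × (0.170 − 0.196)/0.788 = 7.63

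The gap shrinks to about 0.6 day, and r × gap to 0.06-0.18 log10.

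Simulated trials with no treatment effect (30 per arm, SD of change 0.7-1.0 log10 at a given day, two-sided 5% t-test on last-specimen change, 6-minute timing) give:

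| Specimen days | False difference (log10) | Type I error |
|---|---|---|
| Limited to 1-14 (truncated) | about 0.05-0.20 | about 6-9% |
| Not limited | about 0.15-0.43 | about 7-16% |

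Moving out-of-range days to the limits, instead of truncating, gives values between these two rows. The decline rate and SD are assumptions; no document supplies them.

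**5. Cost of lost pairs.** The detectable difference is (1.96 + 0.84) × √(2/n) SD: 0.72 SD with 30 per arm, 0.79 with 25 and 0.89 with 20. Power for 0.72 SD falls from 80% to about 73% and 63%.

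**The case against.** The strongest reply has four parts.

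- **Sampling is bounded and time is mentioned.** Specimens are confined to Week 1, perhaps Week 2, and the analysis is to be done over time, so a sensible analyst might bring in specimen day. The bound stands and roughly halves the illustrated bias. The wording still does not say how time enters, and ANOVA by occasion needs occasions that this sampling lacks.
- **The preliminary data are weak support.** They are retrospective and used polyhexanide with dwell times, not continuous saline. From the printed means and SDs, the timing gap gives t = 1.43/(5.2 × √(1/74 + 1/34)) = 1.33, p about 0.19 (printed 0.04; a rank test could differ). This stands. The table shows only that counts and timing could differ by arm.
- **The study is partly meant to gather data for a larger trial.** True, but a reduction over undefined intervals is poor planning information too.
- **A mixed model does not remove outcome-driven sampling.** This also stands; the assumption has to be stated and tested.

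A reader might go further and infer that the fastest responders have no follow-up specimen. The documents do not support that: a wound closed in hospital has a subsequent inpatient surgery, and those without a specimen include subjects sent home on NPWT because the wound is not ready. Nor does it follow that the bias must run against irrigation, or that a particular share of subjects would drop out of a three-occasion model, since the plan specifies no such model. The ANOVA sentence does not name gene expression, so no ANOVA is stated for Objective 3.

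**Conclusion.** The concern holds. The endpoint has no time point, two sections disagree on which specimens are taken, and the stated analysis presumes a common sampling schedule that neither section provides. Following the plan as written compares changes over unequal, wound-driven intervals and can lose subjects who have only a Day 0 specimen.

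The direction and size of any bias cannot be fixed from the documents. The figures in step 4 are illustrations. They rest on an assumed common decline, an assumed SD, last-specimen change, and timing borrowed from a different irrigation regimen. They isolate timing; selective availability of specimens could add to the bias or offset it.

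This should be corrected before analysis. It affects the primary endpoint of a named objective, though not the wound-volume comparisons of Objective 1.

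**What to change.** 1. Make the Inpatient Tissue Samples text and the Schedule of Events row agree on which specimens are taken, including those after wound recurrence, which the Schedule does not show.
2. For Objective 2, replace the ANOVA of changes with a mixed model for log10 total load, using the actual day of each specimen since Day 0, arm-by-time terms and a common baseline mean. Include all randomised subjects of the two arms compared, and keep those with Day 0 only.
3. Pre-specify as primary one model-based arm difference at a fixed day within the inpatient window, chosen before any data are seen by arm.
4. State that the Microbial Diversity methods address bacterial composition and are separate from this load analysis.
5. Report specimen counts, specimen days and number of surgeries by arm.
6. Add a simple sensitivity analysis, for example repeating the contrast with loads for subjects lacking follow-up shifted up and down by stated amounts.

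The same time-adjusted model can serve Objective 3, which uses the same specimens.

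The cost is SAP wording and modest analysis time, with no added specimens and no change to care. The downside is reliance on a smooth trajectory between specimens and on missingness being explained by observed load. Because repeat debridement follows wound state, the second assumption is not guaranteed, hence item 6.
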